- Changes in the QoL of patients suffering from acute or chronic hemorrhoids, who received conservative treatment, within 1 month after presenting to a doctor.
- Changes in the QoL of patients suffering from acute or chronic hemorrhoids, who received combination treatment, within 1 month after presenting to a doctor.
- Changes in the QoL of patients suffering from acute or chronic hemorrhoids, who underwent minimally invasive interventions, within 1 month after presenting to a doctor.
- Changes in clinical manifestations in patients suffering from acute or chronic hemorrhoids, and their association with demographic and clinical parameters, as well as the chosen treatment strategies (surgical, minimally invasive, or conservative).
- Patient's compliance with recommendations of a doctor.

Design:

The EQUALISER program is a Russian, multicenter, observational program.

In Russia, the program is scheduled for 2018-2019. It is expected that 90 doctors will take part in the program in 60 cities of the Russian Federation. The planned number of patients is 900. Each participating doctor includes at least 10 patients and fills out an electronic case report form (CRF). All treatment is carried out in accordance with the instructions for medical use and routine clinical practice.

| | |
|------------------------------------|---------|
| First visit of the first patient | 02/2019 |
| Last visit of the last patient | 05/2019 |
| Completion of statistical analysis | 08/2019 |
| Preliminary report | 12/2019 |
| Final report | 03/2020 |

Methods:

During the program, at each visit the leading clinical symptoms of hemorrhoids will be assessed.

The quality of life assessment will be carried out using the validated questionnaire SF36 (in Russian) (**Appendix 2**)

Inclusion visit (V0)

Patients who meet the inclusion criteria will be included in the program, and for them the CRF will be completed.

Visit 1 (V1) Surgical intervention (if applicable).

Visit 2 (V2) in 5-7 days after surgical intervention or 5-7 days after the Inclusion Visit (V0), if intervention was not performed.

Visit 3 (V3) in 25-30 days after surgical intervention or 25-30 days after Inclusion Visit (V0), if intervention was not performed.

| Visit | Actions |
|-------|---|
| V0 | 
 • Signing the Informed Consent Form |

| | |
|----|--|

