- Change in the proportion (in %) of patients with bleeding events or prolapse of hemorrhoids among patients suffering from acute or chronic hemorrhoids, within 1 month after presenting a doctor, and its relationship to demographic, clinical parameters and the chosen treatment strategies (surgical, minimally invasive, and conservative).
- Proportion (%) of patients compliant with recommendations on lifestyle changes
- Proportion (%) of patients compliant with recommendations on medical therapy.

Statistical analysis:

Baseline characteristics will be analyzed in all included patients despite adherence to the protocol. Analysis of the results of program will be performed using the SPSS 12.0 software package (SPSS Inc., USA). The data entry errors will be corrected before the statistical processing. Quantitative parameters will be presented depending on the distribution of primary data as arithmetic mean \pm standard deviation for parametric variables, or as median (25; 75 percentiles) for nonparametric variables. Multiple comparisons will include adjustments for continuity.

Changes in the quantitative parameters during the follow-up period will be evaluated using the Student's t-test for paired samples or its nonparametric analogue, Wilcoxon test. Differences on the quantitative parameters, both between the independent groups and during the follow-up, will be evaluated as the mean difference with the corresponding 95% confidence interval.

Comparisons of changes on the VAS scales and the Rome III constipation scale will be carried out using two-factor analysis of variance (ANOVA) with repeated measures to compare the scores before and after the treatment.

Adverse events will be recorded and analyzed in patients with the reporting of all the AEs, SAEs, ADRs, SADRs and special situations.

Administrative considerations

The right to own the documentation, data and results of the program.

The sponsor reserves the exclusive rights for all materials, information, unpublished documentation, results and information received during the program. The sponsor reserves the right to send data on the program (case report forms, results of analyses, and reports) to health authorities.

No unpublished documentation or information transmitted to investigators can be transferred to unauthorized persons without the prior written consent of the Sponsor.

Publication and communication

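### Quantitative change is analysed only in patients with the follow-up value; the plan has no rule for a missed V3 and leaves the V2 data of those patients unused

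*Combined protocol and SAP*

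**What the plan says.** All references are to the combined protocol and SAP.

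- **Analysis set.** The only statement, under Statistical analysis, is: "Baseline characteristics will be analyzed in all included patients despite adherence to the protocol". No set is named for any outcome.
- **Within-patient change.** Changes in quantitative parameters over follow-up are "evaluated using the Student's t-test for paired samples or its nonparametric analogue, Wilcoxon test".
- **VAS and Rome III.** These are compared by a two-factor ANOVA "with repeated measures to compare the scores before and after the treatment". The time points are not listed.
- **Visit table (Methods).** SF-36 appears at V0 and V3, not at V2. Pain, itching and discomfort are recorded at V0 with the VAS appendix cited, and the V2 row names VAS explicitly. The V3 row lists clinical manifestations without naming VAS. Rome III appears at V0 only.
- **Size (Design).** "The planned number of patients is 900". "It is expected that 90 doctors will take part in the program in 60 cities of the Russian Federation", and "Each participating doctor includes at least 10 patients".
- **Withdrawal (Treatment).** Patients may refuse to continue, but no rule covers their data.

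The plan gives no expected dropout rate, missing-data method, comparison of completers with non-completers, or sensitivity analysis.

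**The concern.** When a plan names no outcome set, the test decides who is analysed. A paired t-test or Wilcoxon test drops anyone without both values. A classical repeated-measures ANOVA drops anyone lacking a time point in the model. The baseline table would then describe everyone included, while the change results describe those who came back at day 25-30.

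In routine care, coming back may depend on how the patient is doing. If it does, mean change in completers is not mean change in the included patients, and a narrow interval from several hundred pairs is centred on the wrong value. The V2 symptoms and VAS could predict both return and recovery, and the planned tests make no use of them for a patient who misses V3.

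The point is limited to quantitative change. Bleeding, prolapse and compliance proportions are not assigned to these tests.

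**Working it through.** **1. The plan's own figure.** 90 doctors x 10 patients = 900. It reproduces as a recruitment count. No power, SD or dropout allowance stands behind it.

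**2. Pairs available.** With a proportion d missing V3, pairs = 900 x (1 - d).

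**3. Bias.** Completer bias in mean change = d x gap, where the gap is mean change in completers minus mean change in those lost. For a 5-point gap this gives 0.25 at 5% loss, 1.0 at 20% and 1.5 at 30%. For a 10-point gap it gives 0.5, 2.0 and 3.0.

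**4. A worked mechanism.** All of these inputs are assumptions: SD of change 20, V2 VAS correlated -0.4 with change, everyone has a V2 value, and the log-odds of missing V3 rise by 0.7 per SD of V2 VAS. At 15% loss, simulation puts the V2 VAS of lost patients 0.656 SD above that of completers. Then:

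- gap = 20 x 0.4 x 0.656 = 5.25
- bias = 0.15 x 5.25 = 0.79
- standard error = 20/√765 = 0.723, so the bias is 0.79/0.723 = 1.09 standard errors
- coverage = Φ(1.96 - 1.09) - Φ(-1.96 - 1.09) = 0.81

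Simulation of 900 patients agrees:

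| Loss at V3 | Pairs | Bias (points) | 95% half-width | Coverage |
|---|---|---|---|---|
| 5% | 855 | 0.27 | 1.34 | 93-94% |
| 10% | 810 | 0.5 | 1.38 | 87-88% |
| 15% | 765 | 0.8 | 1.42 | 80-82% |
| 20% | 720 | 1.0-1.1 | 1.46 | 70-71% |
| 30% | 630 | 1.5 | 1.56 | 51-52% |

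Improvement is overstated when the worse patients at V2 are lost, and understated when the better ones are.

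**5. Weaker or no selection.** At 15% loss, halving the log-odds (0.35) or the correlation (-0.2) gives a bias of about 0.4 and coverage of 91-93%. Random loss, or loss rising equally at both ends of V2 VAS, gives zero bias and about 95% coverage.

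**6. What V2 adds.** Regressing change on V2 VAS and averaging over everyone brings the bias to about 0 in each setting of steps 4 and 5. A separate VAS simulation used a true change of -35 mm, SD 20 per visit, log-odds of loss 0.05 per mm of V2 VAS (1.0 per SD) and 10-30% loss:

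| Analysis | V0-V2 correlation 0.5 | V0-V2 correlation 0.3 |
|---|---|---|
| Paired completers | -35.2 to -35.5 | -35.5 to -36.6 |
| Model with V0, V2, V3 | -35.0 to -35.1 | -35.0 to -35.1 |
| Model with V0, V3 only | -35.8 to -37.1 | -36.0 to -37.8 |

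A model that leaves out V2 does not repair the bias, and here it did worse than the paired analysis.

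**7. The ANOVA.** If it uses V0, V2 and V3, and 10% miss V2 and 15% miss V3 independently, it keeps 900 x 0.90 x 0.85 = 688 (688.5), against 765 with V0 and V3. That is about 77 fewer. If it uses one value before and one after treatment, nobody is lost for missing V2.

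**The case against.** - **The plan never says completers only.** True. That follows from the named tests and the absence of any other rule. It is a gap by silence, but it still determines who is analysed.
- **Selection is not shown.** True. The documents give no attendance figures, and loss unrelated to outcome, or balanced at both ends, costs precision only. This makes the bias conditional.
- **The effect is small.** A bias of 0.8 is 0.04 of the assumed SD and lies within the half-width of about 1.4, and no decision threshold depends on it. This stands, and it keeps the point at the level of a cheap improvement. What suffers is the stated 95% confidence.
- **V2 has no SF-36.** True. For quality of life, V2 can serve only as a predictor in an imputation model.

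A reader might also infer four stronger things that the documents do not support:

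- That many patients lost at V3 have V2 data. V2 is scheduled, but its attendance is not reported.
- That bias differs by strategy because operated patients are followed more closely. Methods gives the same 5-7 and 25-30 day windows to both groups, counted from surgery or from V0, and the only extra visit is the operation itself.
- That the ANOVA discards patients who miss only V2, or relies on equal variances of differences. Both need a three-visit reading. The wording on scores before and after treatment more naturally means two occasions, for which that variance condition holds automatically.
- That every outcome is affected. The proportions have no named test.

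**Conclusion.** The concern holds for quantitative change. SF-36 change, as scheduled, rests on patients who attend V3; the plan says nothing about the rest, and scheduled V2 information that could help goes unused.

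The size cannot be read from the documents. Under the stated assumptions the bias runs from zero (random or symmetric loss), through 0.3 points at 5% loss and 0.8 at 15%, to 1.0-1.1 at 20%. Coverage falls from about 95% to about 71% over that range. These figures assume that V2 VAS is available for everyone; patients who also miss V2 can be informed only by V0. They also assume that loss depends on V2 rather than directly on the unseen V3 value, in which case adjustment would not fully remove the bias.

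**What to change.** 1. Define the outcome set as all included patients with a V0 value of the measure concerned.
2. For SF-36 change, use multiple imputation, or a joint model, with V0 covariates and V2 VAS and symptoms as predictors. Keep the paired completer result as a sensitivity analysis. Statistical parameters names the EQ-5D index where the endpoints and visit table name SF-36, so reconcile the instrument first.
3. For VAS, replace the repeated-measures ANOVA with a linear mixed model on all available visits, including V2: visit, strategy, visit-by-strategy, unstructured covariance. First confirm that VAS is recorded at V3.
4. Report V3 completion, and the baseline features of patients with and without V3, by strategy.
5. State the time points of the Rome III comparison, which has no scheduled value after V0.

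The cost is analysis wording and modest programming, with no new visits. The downside is reliance on data missing at random given V0 and V2. A sensitivity analysis allowing for loss not at random would show how far the result depends on that.

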APPENDIX 2 SF36 Questionnaire

SF-36 QUESTIONNAIRE

Name: _____

Ref. Dr: _____

Date: _____

ID#: _____

Age: _____

Gender: M / F

Please answer the 36 questions of the Health Survey completely, honestly, and without interruptions.

GENERAL HEALTH:

In general, would you say your health is:

Excellent Very Good Good Fair Poor

Compared to one year ago, how would you rate your health in general now?

Much better now than one year ago
 Somewhat better now than one year ago
 About the same
 Somewhat worse now than one year ago
 Much worse than one year ago

LIMITATIONS OF ACTIVITIES:

The following items are about activities you might do during a typical day. Does your health now limit you in these activities? If so, how much?

Vigorous activities, such as running, lifting heavy objects, participating in strenuous sports.
 Yes, Limited a lot Yes, Limited a Little No, Not Limited at all

Moderate activities, such as moving a table, pushing a vacuum cleaner, bowling, or playing golf
 Yes, Limited a Lot Yes, Limited a Little No, Not Limited at all

Lifting or carrying groceries
 Yes, Limited a Lot Yes, Limited a Little No, Not Limited at all

Climbing several flights of stairs
 Yes, Limited a Lot Yes, Limited a Little No, Not Limited at all

Climbing one flight of stairs
 Yes, Limited a Lot Yes, Limited a Little No, Not Limited at all

Bending, kneeling, or stooping
 Yes, Limited a Lot Yes, Limited a Little No, Not Limited at all

Walking more than a mile
 Yes, Limited a Lot Yes, Limited a Little No, Not Limited at all

Walking several blocks
 Yes, Limited a Lot Yes, Limited a Little No, Not Limited at all

Walking one block
 Yes, Limited a Lot Yes, Limited a Little No, Not Limited at all

Have you felt downhearted and blue?

- All of the time
- Most of the time
- A good Bit of the Time
- Some of the time
- A little bit of the time
- None of the Time

Did you feel worn out?

- All of the time
- Most of the time
- A good Bit of the Time
- Some of the time
- A little bit of the time
- None of the Time

Have you been a happy person?

- All of the time
- Most of the time
- A good Bit of the Time
- Some of the time
- A little bit of the time
- None of the Time

Did you feel tired?

- All of the time
- Most of the time
- A good Bit of the Time
- Some of the time
- A little bit of the time
- None of the Time

SOCIAL ACTIVITIES:

During the past 4 weeks, how much of the time has your physical health or emotional problems interfered with your social activities (like visiting with friends, relatives, etc.)?

- All of the time
- Most of the time
- Some of the time
- A little bit of the time
- None of the Time

ENERGY AND EMOTIONS:

These questions are about how you feel and how things have been with you during the last 4 weeks. For each question, please give the answer that comes closest to the way you have been feeling.

Did you feel full of pep?

- All of the time
- Most of the time
- A good Bit of the Time
- Some of the time
- A little bit of the time
- None of the Time

Have you been a very nervous person?

- All of the time
- Most of the time
- A good Bit of the Time
- Some of the time
- A little bit of the time
- None of the Time

Have you felt so down in the dumps that nothing could cheer you up?

- All of the time
- Most of the time
- A good Bit of the Time
- Some of the time
- A little bit of the time
- None of the Time

Have you felt calm and peaceful?

- All of the time
- Most of the time
- A good Bit of the Time
- Some of the time
- A little bit of the time
- None of the Time

Did you have a lot of energy?

- All of the time
- Most of the time
- A good Bit of the Time
- Some of the time
- A little bit of the time
- None of the Time

Bathing or dressing yourself

Yes, Limited a Lot Yes, Limited a Little No, Not Limited at all

PHYSICAL HEALTH PROBLEMS:

During the past 4 weeks, have you had any of the following problems with your work or other regular daily activities as a result of your physical health?

Cut down the amount of time you spent on work or other activities
 Yes No

Accomplished less than you would like
 Yes No

Were limited in the kind of work or other activities
 Yes No

Had difficulty performing the work or other activities (for example, it took extra effort)
 Yes No

EMOTIONAL HEALTH PROBLEMS:

During the past 4 weeks, have you had any of the following problems with your work or other regular daily activities as a result of any emotional problems (such as feeling depressed or anxious)?

Cut down the amount of time you spent on work or other activities
 Yes No

Accomplished less than you would like
 Yes No

Didn't do work or other activities as carefully as usual
 Yes No

SOCIAL ACTIVITIES:

Emotional problems interfered with your normal social activities with family, friends, neighbors, or groups?

Not at all Slightly Moderately Severe Very Severe

PAIN:

How much bodily pain have you had during the past 4 weeks?

None Very Mild Mild Moderate Severe Very Severe

During the past 4 weeks, how much did pain interfere with your normal work (including both work outside the home and housework)?

Not at all A little bit Moderately Quite a bit Extremely

GENERAL HEALTH:

How true or false is each of the following statements for you?

I seem to get sick a little easier than other people
 Definitely true Mostly true Don't know Mostly false Definitely false

I am as healthy as anybody I know
 Definitely true Mostly true Don't know Mostly false Definitely false

I expect my health to get worse
 Definitely true Mostly true Don't know Mostly false Definitely false

My health is excellent
 Definitely true Mostly true Don't know Mostly false Definitely false

APPENDIX 3. The Rome III diagnostic criteria for the constipation

| Symptoms | Characteristics of the symptoms |
|---|---|
| 1. Straining during at least 25% of defecations | Symptoms should be observed within 12 weeks (not necessarily consecutive) during the previous year. |
| 2. Lumpy or hard stools in at least 25% of defecations | Syndrome must include two or more of the symptoms listed in this table. |
| 3. Sensation of incomplete evacuation for at least 25% of defecations | |

| | |
|---|--|
| 4. Sensation of anorectal obstruction/blockage for at least 25% of defecations | |
| 5. Manual maneuvers to facilitate at least 25% of defecations (e.g., digital evacuation, support of the pelvic floor) | |
| 6. Fewer than three defecations per week | |

APPENDIX 4

Classification of internal hemorrhoids (Goligher's classification)

*Assessment criteria:

- Grade I Hemorrhoids are prolapsed only into the anal canal.
- Grade II Bleeding and prolapse of hemorrhoids. Hemorrhoids spontaneously reduce after defecation.
- Grade III Prolapse of hemorrhoids after defecation requires their manual reduction.
- Grade IV Prolapse of hemorrhoids that cannot be reduced into the anal canal.

APPENDIX 5.

Example of wording of the diagnosis statement (National guidelines on coloproctology, 2015)

- Internal hemorrhoids (II- 3, III- 7, II-11)
- External (3A, 7B) and internal hemorrhoids (II- 3, III- 7, II-11)
- External hemorrhoids, complicated by an acute thrombosis of grade 2 (7 o'clock).

APPENDIX 6.

Visual analogue scale (VAS)

«Not at all»

«Most severe ... ever experienced»

_____ , _____ cm *
